6.1.1.3 Renal/Genitourinary

Acute toxicity of the urinary tract is manifested by cystitis. Maintaining high fluid intake is important. Bladder antispasmodics, analgesics and antibiotics are recommended. Hematuria is not usually seen with acute cystitis and suggests bladder invasion by tumor. Acute vulvovaginitis is

seen when the pelvic fields extend inferiorly to include the vulvoperineal area. Treatment of acute vulvoperineal reaction may require warm saline soaks, wearing loose clothing and keeping the area dry. Topical steroids and treatment interruption may be necessary also (Refer to [Section 6.1.2](#)).

6.1.1.4 Dermatologic/Skin (Cutaneous)

With the use of megavoltage external beam radiation therapy, skin reactions in the treatment field are infrequent. However, cutaneous reactions are more likely to develop if sites such as the inguinal area, vulva, and the perineum are in the radiation fields. During radiation therapy, mild irritation and redness of the skin may occur within the radiation fields. Some participants may experience more intense skin reaction such as dry or moist desquamation depending upon the energy of the megavoltage beam, number of fields used per day, need to cover distal vagina and therefore flashing perineum and use of chemotherapy. Hair loss in the pubic area may occur which can be permanent. Late subcutaneous fibrosis, telangiectasia, and skin atrophy are uncommon sequelae.

Almost all participants with vulvar/perineal skin in the treatment fields can expect to develop acute moist desquamation during the course of external beam radiation therapy.

Acute skin reactions may be treated according to the institutional preferences. Aquaphor or steroid creams may be used for CTCAE v4.0 Grade 1-2 reactions and it is not necessary to interrupt the radiation therapy. For CTCAE v4.0 Grade 3-4 skin reactions when generalized macular, papular or vesicular eruptions have developed, or there is generalized exfoliative or ulcerative dermatitis in the treatment fields, radiation therapy should be interrupted until skin reaction improves to Grade 2 or better. Treatment may require symptomatic management of pain, use of warm saline soaks, coating ointments, wearing loose clothing, and keeping the area dry. Radiation therapy should be resumed as soon as the skin reactions have improved to no worse than Grade 2.

The Study Chair should be notified of any Grade 4 toxicity (Refer to [Section 6.1.2](#)).

6.1.2 Radiation Dose Modifications

6.1.2.1 Blood Bone Marrow (Hematologic) Adverse Effects

External RT will be delayed for $ANC \leq 1000/\text{mm}^3$ ($1.0 \times 10^9/\text{L}$) or platelet count $\leq 50,000/\text{mm}^3$ ($50.0 \times 10^9/\text{L}$). External RT may continue if $ANC < 1000/\text{mm}^3$ and platelets are $> 50,000/\text{mm}^3$. If external RT is delayed, counts will be obtained twice weekly while participant is on

break and treatment resumed when counts are ANC > 1000/mm³ and platelets > 50,000/mm³. If longer than a two-week break is required, the Study Chair should be contacted during this break.

Febrile neutropenia requiring intravenous antibiotics or thrombocytopenia with bleeding requiring platelet transfusion will require holding radiation therapy until symptoms resolve (fever or bleeding) and the hematologic parameters described above are met.

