4.2 Cancer Treatment Therapies

4.2.1 Radiation Therapy

See dose table below [\(Section 4.6\)](#) for details and appropriate fractionation schemes.

- 41.4-45.0 Gy/1.8 Gy per fraction/23-25 fractions/five weeks pelvic RT.
- 35-43.6 Gy intracavitary brachytherapy in one to two implants LDR or 18-28 Gy intracavitary brachytherapy in 2-4 fractions HDR.
- 5.40 - 9.00 Gy/1.8 Gy/3-5 fractions/3-5 days parametrial boost to involved parametria.
- Overall treatment time not to exceed eight weeks.

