6.1.1.1 Blood/Bone Marrow (Hematologic)

Hematologic toxicity is seen infrequently unless pelvic radiation is accompanied by chemotherapy. A CBC should be obtained weekly, and if the ANC falls below $1500/\text{mm}^3$ ($1.5 \times 10^9/\text{L}$) or the platelet count drops below $100,000/\text{mm}^3$ ($100.0 \times 10^9/\text{L}$), counts should be obtained twice weekly. Treatment may proceed if $\text{ANC} > 1000/\text{mm}^3$ ($1.0 \times 10^9/\text{L}$), and platelet count $> 50,000/\text{mm}^3$ ($50.0 \times 10^9/\text{L}$).

Every effort should be made to maintain hemoglobin $\geq 10\text{g/dL}$ (6.2 mmol/L). It is up to the individual investigator's discretion as to how best to achieve this.

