6.2.3 Dose Modifications for Cisplatin

If different dose levels for cisplatin are required because of two different types of toxicities, use the dose level requiring the greatest reduction. There will be no dose re-escalation once the cisplatin is dose reduced.

The following levels should be used for cisplatin dose reductions:

Dose Level 0	Dose Level -1	Dose Level -2
40 mg/m^2	30 mg/m^2	25 mg/m^2

There will be no dose reduction below dose level -2 (i.e. cisplatin will be discontinued if further toxicity occurs).

Chemotherapy should not be administered during a radiation therapy delay.

All chemotherapy-related toxicities will also be graded according to the Common Toxicity Criteria (CTCAE v4.0).

Radiotherapy will not be omitted or delayed for chemotherapy-related toxicities unless the investigator considers that the participant is too sick to be treated.

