6.2.4 Cisplatin Modifications

6.2.4.1 Blood/Bone Marrow (Hematologic) Adverse Effects

Granulocyte, ANC or Platelet Counts

Based on counts within 2 days prior to each scheduled cisplatin dose, give the following:

ANC or granulocytes/μL		Platelets/μL	Cisplatin
$\geq 1,500$	and	$\geq 100,000$	No Dose Reduction
1,499-1,000	or	99,999-75,000	Reduce by one dose level*
< 1,000	or	< 75,000	Hold*

Treatment should resume as soon as recovery from toxicity allows. If treatment is delayed for >2 weeks, notify the Study Chair. External RT should continue while drug is withheld.

*If the maximum number of prior dose reductions of cisplatin have been made, treatment may be held for up to two weeks for blood count recovery. Treatment will resume at the same dose level as there are no more dose reductions allowed.

Nadir blood counts or febrile neutropenia

For nadir neutropenia in the absence of fever or with fever which is successfully treated by oral antibiotics, there will be no dose adjustment.

Hold cisplatin during febrile neutropenia. For febrile neutropenia (ANC $\leq 500/\text{mm}^3$ ($0.5 \times 10^9/\text{L}$) and temperature $\geq 100.5^\circ\text{F}$ or 38°C) requiring intravenous antibiotics, the dose of cisplatin should be reduced by 1 dose level for the next and subsequent doses of chemotherapy.

For Grade 4 nadir thrombocytopenia (platelets $\leq 10,000$ ($10.0 \times 10^9/\text{L}$)), the dose of cisplatin should be reduced by 1 dose level for the next dose and for all subsequent doses of chemotherapy.

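### At platelets ≤50,000/mm³, and less cleanly at ANC <1000/mm³, 6.1.2.1 delays external RT while 6.2.4.1 and 6.2.3 keep it going, and no text says which governs

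*Combined protocol and SAP*

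**What the plan says.** All references are to the combined protocol and SAP.

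- **6.1.2.1 (radiation modifications, hematologic).** "External RT will be delayed for $ANC" ≤1000/mm³ or platelets ≤50,000/mm³, with "treatment resumed when counts are ANC > 1000/mm³ and platelets > 50,000/mm³". Between these two rules, a second sentence as printed lets external RT go on at ANC <1000 with platelets >50,000.
- **6.1.1.1 (expected hematologic toxicity).** "Treatment may proceed if" ANC is above 1000 and platelets are above 50,000, the same limits as the resume rule.
- **6.2.4.1 (cisplatin modifications, hematologic).** Cisplatin is held at ANC <1,000 or platelets <75,000. Below the count table stands: "External RT should continue while drug is withheld". No lower count limit is attached.
- **6.2.3 (cisplatin dose modifications).** "Radiotherapy will not be omitted or delayed for chemotherapy-related toxicities unless the investigator considers that the participant is too sick to be treated". The same section adds: "Chemotherapy should not be administered during a radiation therapy delay".
- **Complicated cytopenia (6.1.2.1).** "Febrile neutropenia requiring intravenous antibiotics or thrombocytopenia with bleeding requiring platelet transfusion will require holding radiation therapy", until symptoms resolve and the counts recover.
- **Time limits.** Section 4.2.1: "Overall treatment time not to exceed eight weeks". Sections 4.6.1.3 and 4.6.8 give 56 days, and 6.1 calls 56 days a goal. Section 6.1.3 takes participants off protocol therapy after a break of more than three weeks.

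**The concern.** A site that sees platelets of 45,000 is told by the radiation section to stop external RT and by the drug section to carry on with it. It cannot do both. Cisplatin is withheld on either reading, so the open question is only whether RT stops too.

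Two things are at stake. One is safety: pelvic RT either continues or stops in a woman with low counts, depending on which page the site opens. The other is RT duration, which the protocol caps and which 6.1 links to survival. In a 45-woman feasibility study, different handling of identical counts across sites would also blur what regimen was actually delivered.

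**Working it through.** No stated figure has to be reproduced, because this is a conflict between rules. The check applies each rule to the same counts.

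| ANC (/mm³) | Platelets (/mm³) | 6.1.2.1, first sentence | 6.1.2.1, second sentence as printed | 6.2.4.1 | Result |
|---|---|---|---|---|---|
| 1200 | 45,000 | delay RT | not triggered | hold cisplatin, RT continues | conflict |
| 1600 | 50,000 | delay RT | not triggered | hold cisplatin, RT continues | conflict |
| 900 | 60,000 | delay RT | RT may continue | hold cisplatin, RT continues | conflict, and 6.1.2.1 contradicts itself |
| 900 | 120,000 | delay RT | RT may continue | hold cisplatin, RT continues | conflict, and 6.1.2.1 contradicts itself |
| 1000 | 60,000 | delay RT | not triggered | hold cisplatin (platelets), RT continues | conflict |
| 1000 | 120,000 | delay RT | not triggered | reduce one level, no hold | no conflict with 6.2.4.1 |
| 1200 | 60,000 | no delay | not triggered | hold cisplatin, RT continues | agree |
| 1600 | 120,000 | no delay | not triggered | full dose | agree |

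**Where the conflict lies.** At platelets ≤50,000 it is clean: no doubtful character is involved. At ANC <1000 with platelets >50,000 the first sentence of 6.1.2.1 still conflicts with 6.2.4.1, but the second sentence as printed sides with 6.2.4.1. The printed < is probably a reversed sign, since both the resume rule and 6.1.1.1 require ANC >1000. It could also be an artefact of text extraction.

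**Is there a tie-break?** The only one in 6.2.3 concerns competing cisplatin dose levels. None covers RT delay.

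**RT time.** Section 4.6.1.2.1 (LDR) allows 35 days of whole-pelvis RT plus 3 weeks for brachytherapy: 35 + 21 = 56.
- A hold of 7, 14 or 21 days leaves 21 − 7 = 14, 21 − 14 = 7 or 21 − 21 = 0 days for brachytherapy.
- From the planned Day 50 finish in 4.6.8, a 7-day hold gives 50 + 7 = Day 57, one day over, unless brachytherapy is compressed.
- Under HDR, 4.6.1.2.4 says brachytherapy should start by week 4, so there is more slack.

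**Cisplatin.** Assume one weekly dose is held on Day 15, 22 or 29 and made up at the next weekly slots. The slots are Days 1, 8, 15, 22, 29, 36 and 43. Dropping one leaves six, the last on Day 43. This is so whether RT continues or is delayed 7 days. Day 43 precedes Day 50, so the bar in 6.2.6 on chemotherapy after RT ends is not reached and no cycle is lost.

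**Secondary check, 6.2.5.** The mg/dL formula has denominator 72 × creatinine and gives mL/min; mL/s needs a further factor of 60.
- The protocol equates 2.0 mg/dL with 177 µmol/L, so the µmol/L constant is 72 × 60 / (177/2.0) = 48.8.
- 72 × 60 × 11.3 = 48816 is the constant for mmol/L.
- Example (assumed age 45, 60 kg, creatinine 1.5 mg/dL = 133 µmol/L): the numerator is 95 × 60 × 0.85 = 4845. The mg/dL formula gives 4845/(72 × 1.5) = 44.9 mL/min = 0.75 mL/s. As printed, 4845/(48816 × 133) = 0.00075 mL/s; with 0.133 mmol/L it is 0.746 mL/s.

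**The case against.** The best defence is that the specific rule governs. Section 6.1.2.1 sits under radiation modifications, sets numeric limits and is mandatory; the opposing sentence in 6.2.4.1 sits under drug therapy and is advisory. Section 6.2.3 itself foresees RT delays and has an exception for a participant too sick to treat. On this reading 6.2.4.1 means only that holding cisplatin is not in itself a reason to stop RT, and it keeps a use at platelets between 50,000 and 75,000 with ANC >1000.

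That reading is plausible, and a site may well adopt it, but the protocol does not state it. The 6.2.4.1 sentence is also in a hematologic subsection, directly tied to a count table. The RT-delay range for ANC (≤1000) covers the whole cisplatin-hold range (<1000), so under this defence the sentence would never apply to a neutropenia hold. A participant with an ANC of 900 and no symptoms meets the numeric trigger without being too sick.

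Existing safeguards narrow the gap. Febrile neutropenia needing intravenous antibiotics and bleeding needing platelet transfusion have their own RT hold. The Study Chair is contacted for breaks over two weeks, and 4.6.1.1 requires a documented reason if pelvic RT exceeds 38 days, which a 7-day hold on a 35-day plan would trigger (35 + 7 = 42). These leave uncomplicated low counts open.

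A reader might also infer that the conflict distorts the primary measure, because cisplatin cannot be given during an RT delay or after RT ends. The documents do not support that: the schedule above delivers all six doses by Day 43 either way. That schedule assumes held doses are made up weekly. The plan tracks missing doses separately, so some may simply be missed, and no expected frequency of such counts is given.

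**Conclusion.** The concern holds as an internal contradiction in a safety-relevant rule, not as a mere lack of detail. It is unambiguous at platelets ≤50,000/mm³. A reader might take the ANC <1000 range to be equally clear-cut. It is not, because with platelets >50,000 the text of 6.1.2.1 points both ways, and that branch needs the source PDF before its cause is settled.

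The demonstrated consequence is possible site-to-site inconsistency for uncomplicated low counts, with a bearing on patient safety and the 56-day limit. The size is illustrative: one week's hold moves a Day 50 finish to Day 57 if the rest of the schedule is unchanged, and the 14-, 7- and 0-day remainders apply to the LDR sequence. An effect on cisplatin completion is not shown and cannot be quantified from the documents.

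The 6.2.5 constant is a separate, minor point. It may be an extraction artefact such as a lost decimal point, the mL/min formula beside it is correct, and a result near 0.001 mL/s would probably be noticed.

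**What to change.** 1. In 6.2.4.1 and 6.2.3, add to each RT sentence: *except when the 6.1.2.1 RT hold criteria are met*. If the sponsor's clinicians intend the opposite priority, they should say so in 6.1.2.1. Which rule wins is a clinical decision; the text must state it.
2. After checking the source PDF, print the second sentence of 6.1.2.1 with *ANC > 1000/mm³*.
3. Also after that check, correct the SI denominator in 6.2.5: either 48.816 × creatinine in µmol/L, or keep 48816 and print the unit as mmol/L.

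The cost is one clause in two sections by clarification memo or minor amendment, plus two checks against the source PDF. No extra data or participants are needed.

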6.1.2.2 Gastrointestinal Adverse Effects

Participants will be treated with a low residue diet and anti-peristaltic drugs. External RT will be interrupted for CTCAE v4.0 Grade 3 or 4 GI toxicity. If longer than a two-week break is required, the Study Chair should be contacted during this break. Use of prophylactic antiemetics is strongly recommended.

6.1.2.3 Renal/Genitourinary Adverse Effects

External RT will be delayed for CTCAE v4.0 Grade 3 or 4 bladder toxicity. If longer than a two-week break is required, the Study Chair should be contacted during this break.

6.1.2.4 Dermatologic/Skin (Cutaneous) Adverse Effects

RT will not be delayed for moist desquamation, and if a break is felt to be clinically indicated, the Study Chair should be contacted prior to this break.

6.1.3 Participants with longer than a 3-week break during combined chemotherapy and pelvic radiotherapy, or during brachytherapy will be removed from the protocol-directed therapy. However, they should re-start radiotherapy off study as soon as the toxicities have improved to an acceptable level.

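### Sections 6.1.1.4 and 6.1.2.4 give different instructions on stopping radiotherapy and contacting the Study Chair when a Grade 3-4 generalized skin reaction includes moist desquamation

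*Combined protocol and SAP*

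**What the plan says.** Four places in the combined protocol and SAP bear on this.

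- **Section 6.1.1.4 (skin, under Expected Toxicity).** For Grade 1-2 reactions treated with creams, "it is not necessary to interrupt the radiation therapy". The stop rule begins "For CTCAE v4.0 Grade 3-4 skin reactions when generalized macular, papular or vesicular eruptions have developed, or there is generalized exfoliative or ulcerative dermatitis". It is confined to the irradiated area, and its instruction is that "radiation therapy should be interrupted until skin reaction improves to Grade 2 or better". RT then restarts once the reaction is no worse than Grade 2. On contact, the section says "The Study Chair should be notified of any Grade 4 toxicity" and refers to Section 6.1.2. It lists moist desquamation among the more intense skin reactions without giving it a grade, and adds: "Almost all participants with vulvar/perineal skin in the treatment fields can expect to develop acute moist desquamation".
- **Section 6.1.2.4 (skin, under Radiation Dose Modifications).** This is the only dermatologic rule in Section 6.1.2, and it is one sentence: "RT will not be delayed for moist desquamation, and if a break is felt to be clinically indicated, the Study Chair should be contacted". The sentence ends by placing the contact before the break. It names no grade and does not mention the stop rule in 6.1.1.4.
- **Section 6.1.1.3 (renal/genitourinary).** For acute vulvoperineal reaction, "Topical steroids and treatment interruption may be necessary also", with a reference to Section 6.1.2.
- **Consequences of a break.** Section 6.2.3 says "Chemotherapy should not be administered during a radiation therapy delay". Sections 6.1.3 and 8.1.1 end protocol therapy after a break of more than 3 weeks.

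**The concern.** Sections 6.1.1.4 and 6.1.2.4 are both written as instructions to the site. One says stop and gives the condition for restarting. The other says do not delay, and makes any break subject to prior contact with the Study Chair. A site that meets a severe reaction with moist desquamation can follow either section in good faith and act differently on two matters: whether the beam stops, and whether anyone is called first.

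That bears first on patient safety, because it is a stop-or-continue decision about a severe reaction. It also bears on treatment delivery. An RT delay holds cisplatin. Section 6.2.6 does not allow chemotherapy after RT is complete, and Sections 4.6.1.3, 4.6.8 and 6.1 aim to finish all RT within 56 days. Treatment completion is the primary outcome (Section 11.2), and dose delays and missed doses are tolerability measures (Section 9.1.4). If sites read the rule differently, some variation in these measures would reflect the wording and not the regimen.

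**Working it through.** The documents give no figure on this point, so there is nothing to recompute. The check is to set the rules side by side for each kind of reaction.

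| Reaction | Section 6.1.1.4 | Section 6.1.2.4 | Result |
|---|---|---|---|
| Grade 1-2, with moist desquamation | Interruption not needed | No delay | Agree |
| Grade 3-4 of the described generalized type, no moist desquamation | Interrupt to Grade 2 or better; Study Chair notified if Grade 4 | No bar on delay, but can be read as asking for contact before any skin break | Agree on stopping; unclear on contact |
| Grade 3-4 of the described generalized type, with moist desquamation | Interrupt to Grade 2 or better; Study Chair notified if Grade 4 | No delay, unless a break is judged indicated and the Study Chair is contacted first | Conflict on both stopping and contact |
| Grade 3-4 with moist desquamation, not of the described generalized type | Stop rule not clearly triggered | No delay, with the same exception | No direct conflict |

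The third row is the problem. Four further checks fix its limits.

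1. **Can the two triggers overlap?** The protocol's text makes it plausible. Section 6.1.1.4 treats moist desquamation as one of the more intense skin reactions, and Section 11.4 puts desquamation, generalized eruptions and ulcerative dermatitis in one dermatologic category. How often the overlap occurs cannot be found, because the documents give moist desquamation no grade and do not reproduce the CTCAE criteria.
2. **Does Section 6.1.1.3 conflict as well?** No. It only permits interruption and points to 6.1.2. A site can satisfy it and 6.1.2.4 together by contacting the Study Chair and then pausing.
3. **Does any text set precedence?** No. The cross-reference in 6.1.1.4 is attached to the Grade 4 notification, and 6.1.2.4 neither repeats nor withdraws the stop rule.
4. **Is skin handled like the other toxicities?** No. Sections 6.1.2.1 to 6.1.2.3 use blood-count or grade thresholds and ask for Study Chair contact during breaks longer than two weeks. Section 6.1.2.4 has no threshold and asks for contact beforehand. A site therefore cannot settle the conflict by analogy.

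**The case against.** The strongest defence is that the two sections address different things. Section 6.1.1.4 would be a general rule for severe, generalized dermatitis, and 6.1.2.4 a specific rule for moist desquamation, which the stop sentence does not name. In addition, 6.1.1 is headed as expected toxicity and 6.1.2 as dose modification, and 6.1.1.3 and 6.1.1.4 both refer forward, which suggests that 6.1.2 is operative. Finally, 6.1.2.4 is not a ban: it allows a break after contact.

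Much of this stands, and it confines the point to the overlap. It does not remove the point. Section 6.1.1.4 contains a stop instruction and a restart condition, so it is more than description. No sentence makes 6.1.2 prevail. A reaction that fits both descriptions is not assigned to either rule.

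Three stronger readings are tempting and are not supported:

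- A reader might infer that 6.1.1.3 also orders an interruption that 6.1.2.4 forbids. It is permissive and defers to 6.1.2.
- A reader might infer that the conflict reaches nearly every woman with vulvar or perineal skin in the field. That expected frequency is for moist desquamation of unstated grade. At Grade 1-2 the sections agree, and 6.1.1.4 describes treatment-field skin reactions in general as infrequent.
- A reader might attach a size of 1/38 = 2.6 percentage points (or 1/45 = 2.2) to the completion rate. That is the weight of any one woman among 38 evaluable or 45 enrolled, whatever the cause. Section 11.1 counts completion of cisplatin among those who start it, and Section 6.2.6 lets the sixth cycle be given during brachytherapy, so a short break need not cost a cycle. No text makes exceeding 56 days a failure to complete, and none says that skin breaks reach 3 weeks.

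**Conclusion.** The inconsistency is real and narrow. For a Grade 3-4 skin reaction that meets the 6.1.1.4 description and includes moist desquamation, 6.1.1.4 directs interruption, with notification only at Grade 4. Section 6.1.2.4 directs no delay, with contact before any break. The documents do not say which applies.

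The conclusion rests on reading both sections as operative instructions, and on the two triggers being able to coincide in one woman. The second is plausible from the text, but its frequency is unknown. The effect on treatment completion therefore cannot be estimated, and no number should be given for it. What can be said is that the same reaction could be managed differently at different sites, with cisplatin withheld at one that pauses RT and not at one that continues. The text should be corrected because two stop-or-continue instructions on patient safety should not disagree.

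**What to change.** Reconcile Sections 6.1.1.4 and 6.1.2.4 into one skin rule, and align the cross-reference in 6.1.1.3 with it. The rule should state:

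- whether Grade 3-4 reactions that include moist desquamation fall under the interruption rule or the no-delay rule;
- when the Study Chair is contacted: before a break, on Grade 4 toxicity, or both.

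Which rule applies is for the protocol's clinical team to decide; this point takes no position on it. The change is protocol wording only. It needs no new assessments and no change to the sample size or the analysis.
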